5.5.2 Identity of Investigational Products

Information about the drug formulations to be used in this study is presented in Table 8.

Table 8.	Identity of Investigational Products

Study Drug	Formulation	Route of Administration	Trademark	Manufacturer
Elagolix	Film-coated 300 mg tablets	Oral	N/A	AbbVie
Matching Elagolix Placebo	Film-coated Placebo tablets	Oral	N/A	AbbVie
E2/NETA*	Estradiol 1.0 mg/Norethindrone acetate 0.5 mg capsules*	Oral	N/A	Commercial Tablets: Pharmaceutics International, Inc
Matching E2/NETA Placebo	Placebo capsules	Oral	N/A	AbbVie

* Commercially-available E2/NETA tablets are over-encapsulated to maintain study blinding.

5.5.2.1 Packaging and Labeling

AbbVie will supply blinded study drug in monthly kits (i.e., cartons). Two kits of study drug will be provided at each dispensing visit. One kit consists of Elagolix or matching placebo and the other kit consists of E2/NETA capsules or matching placebo. Each kit contains 5 blister cards, with each blister card containing 7 days of study medication. There are 4 weekly blister cards and 1 extra medication blister card in each kit to supply enough medication for 4 weeks (28 days) of dosing, plus an extra week's supply.

Each individual elagolix or matching placebo blister card contains 14 tablets for a 7-day (weekly) supply study medication. Also, each E2/NETA or matching placebo blister card contains 7 capsules for a 7-day (weekly) supply of study medication.

The kits will be assigned to a subject via IRT and will encode the appropriate study drug to be dispensed at the subject's corresponding study visit.

The kits and blister cards are labeled as per country requirements. All blank spaces on the label will be completed by the site staff prior to dispensing to the subject. Labels must remain affixed to the study drug containers. Adequate supplies of study drug will be provided to each study site automatically via IRT.

5.5.2.2 Storage and Disposition of Study Drug

Elagolix, E2/NETA and respective matching placebo study medication must be stored at controlled room temperature 15° to 25°C (59° to 77°F). Additionally, E2/NETA and matching placebo study medication must be protected from light.

The investigational products are for investigational use only and are to be used only within the context of this study. The study drug supplied for this study must be maintained under adequate security and stored under the conditions specified on the label until dispensed for subject use or returned to AbbVie. Returned study drug should not be re-dispensed to the subject.

5.5.3 Method of Assigning Subjects to Treatment Groups

All subjects will be centrally randomized using an IRT. Before the study is initiated, contact information and user guidelines for IRT will be provided to each site. Study drug will be dispensed at the study visits outlined in Appendix C, Study Activities.

As subjects enter into either the Washout Period or the Screening Period, a unique subject number will be assigned to each subject by the IRT. This unique subject number will be used for each subject throughout the study.

After confirming that the subject has met randomization criteria and prior to the Day 1 (randomization) dose, a unique randomization number will be provided via IRT.

Subjects will be randomly assigned by IRT to receive one of the treatment groups as outlined in Section 5.5.1 for a total of 6 months of treatment.

Study drug must not be dispensed without contacting IRT. Study drug may only be dispensed to subjects enrolled in the study according to kit numbers provided by the IRT.

The randomization schedule will be computer generated by the Statistics Department at AbbVie, North Chicago, IL prior to the start of the study. A copy of all of the

randomization schedules will be kept by the Statistics Department at AbbVie and a copy will be forwarded to the IRT provider.

5.5.4 Selection and Timing of Dose for Each Subject

Selection of the doses used for this study is discussed in Section 5.6.4. Subjects will be randomized into one of the three treatment groups as described in Section 5.5.1.

Study drug will be initiated at the study site on Day 1 (randomization). Subjects will be instructed to self-administer study drug twice a day (once in the morning and once in the evening approximately 12 hours apart) with approximately 8 oz (240 mL) of water. Subjects must return all study drug containers (used or unused) at the subsequent visit.

[figure not shown]
5.5.5 Blinding of Investigational Product

Each active elagolix dose will be identical in appearance to its matched placebo; each active E2/NETA dose will be identical in appearance to its matched placebo. The study site personnel and subject will remain blinded to each subject's treatment throughout the course of the study. The IRT will provide access to blinded subject treatment information during the study.

AbbVie must be notified before the blind is broken, unless identification of the study drug is required for medical emergency; i.e., situation in which the knowledge of the specific blinded treatment will affect the immediate management of the subject/patient's conditions (e.g., antidote is available). AbbVie must then be notified within 24 hours of the blind being broken. The date and reason that the blind was broken must be recorded in the source documents and eCRF, as applicable.

5.5.6 Treatment Compliance

Subjects will be instructed to return all study drug kits (used or unused) to the study site personnel at the Month 1, Month 2, Month 3, Month 4, Month 5 and Month 6 or Premature Discontinuation Visits during the Treatment Period. The study site personnel will document compliance.

The investigator or his/her designated and qualified representatives will dispense study drug only to subjects enrolled in the study in accordance with the protocol. The study drug must not be used for reasons other than those described in the protocol.

Subjects should be advised of the importance of treatment compliance. Study drug should be taken consistently at approximately the same time in the morning and evening each day. Daily recordings of study drug dosing will be obtained using a compliance packaging blister card for all subjects (for both elagolix/matching placebo and E2/NETA/matching placebo). AbbVie will provide training and study drug compliance materials to sites for instructing subjects on study drug compliance.

Sites will be provided scanning technology for direct access to the dosing compliance data; sites are expected to scan all returned blister cards (used/unused/unopened) to obtain the dosing information at each of the Treatment Period visits when study drug is returned to the site by the subject. Any unused/unopened blister cards should be documented as such in the scanning technology source documentation. Sites are expected to use the compliance data to guide them in discussions with the subject regarding compliance. Upon reviewing the dosing data, if the date(s) and time(s) for any of the last 4 doses of study drug (elagolix or E2/NETA or placebo) prior to the monthly Treatment Period visit or Premature Discontinuation visit are missing, the subject will be asked to confirm whether doses were taken and to provide the dates and approximate times of the last 4 scheduled doses prior to the study visit. The subject reported data will be recorded in source and in the eCRF. Sites will document when the blister cards are not returned or when blister cards cannot be scanned.

Sites should instruct subjects not to remove extra or multiple medications from the blister cards all at once and should only remove the study drug from the blister when it is the time to take the dose. If the compliance data shows incidence of removing a number of extra medications, sites should re-train the subjects on the importance of only removing study medication when it is time to take the dose and record re-training in the source documents.

During review of the study drug compliance with the study subject, if the number of tablets/capsules to be taken and the number of tablets/capsules returned do not add up to the number of tablets/capsules dispensed, an explanation should be provided by the subject and recorded in the source documents.

If a subject missed more than 7 consecutive days of taking study drug, the AbbVie TA MD should be notified to determine whether the subject may continue.

Compliance packaging data will be used for exposure response analysis.

5.5.7 Drug Accountability

The study Investigator or designee will verify by signature and date that study drug supplies are received intact and in the correct amounts indicated on the shipping document Proof of Receipt or similar shipping document or via direct recording in IRT. The shipment receipt must be acknowledged in IRT in order to become available for dispensation to subjects. The IRT must also be contacted when any subject discontinues study drug.

The IRT will maintain a current and accurate inventory of all clinical drug supplies, accountability, reconciliation, returns and destruction for each site. The IRT will also include the lot number, kit number, Proof of Receipt number, the number of blister cards/cartons dispensed, initials of person who dispensed the drug, and the date study drug was dispensed for each subject. In addition to using IRT inventory, an accurate inventory of study drug can also be kept by the site.

An overall accountability of the study drug will be performed and verified by the site monitor via IRT throughout the study and at the study site closeout visit. Throughout the study and upon completion or termination of the study, all used and unused containers will be returned to AbbVie according to instructions from AbbVie.

The study investigator or his/her designated representative agrees not to supply study medication to any persons not enrolled in the study or not named as a sub-investigator.

Study drug will be dispensed at the study visits summarized in Appendix C, Study Activities. Returned study drug should not be re-dispensed to the subject.

5.6 Discussion and Justification of Study Design

5.6.1 Discussion of Study Design and Choice of Control Groups

This Phase 3 study will be conducted as a randomized, double-blind, multi-center, placebo-controlled study in premenopausal women 18 to 51 years of age with HMB associated with uterine fibroids. The randomized, double-blind, placebo-controlled study design is the standard for unbiased assessments of treatment group differences.

This study will evaluate the safety and efficacy of elagolix 300 mg BID alone and elagolix 300 mg BID in combination with E2/NETA QD (1.0 mg/0.5 mg) versus placebo in subjects with HMB associated with uterine fibroids. The study will also assess the impact of E2/NETA on the efficacy, safety, and tolerability of elagolix, including hypoestrogenic side effects such as BMD decrease and vasomotor symptoms.

5.6.2 Appropriateness of Measurements

The safety assessments used in this study are standard, widely used and generally recognized as reliable, accurate and relevant within the context of this study design.

Regarding efficacy measures, HMB is the most common symptom of women with uterine fibroids. The quantitation of menstrual blood loss using the alkaline hematin method on sanitary products has been validated by the analytical testing laboratory. Pelvic ultrasound and SIS, are standard methods for assessing uterine fibroid size, fibroid and uterine volume. Endometrial biopsy is a standard method for assessing endometrial safety. DXA is the established gold standard method to assess changes in BMD.

5.6.3 Suitability of Subject Population

Premenopausal women 18 to 51 years of age with HMB (> 80 mL per menstrual cycle) and uterine fibroids were selected for this study because that is the population who suffer

from HMB associated with uterine fibroids. The lower bound of the age limit (18) was chosen based on the relative paucity of adolescent females with symptomatic uterine fibroids prior to age 18, and the upper age of 51 is included to reduce the risk of subjects becoming menopausal during the study. No studies in males or in females outside of the reproductive years are necessary for this proposed indication.

5.6.4 Selection of Doses in the Study

The preliminary results of the 3-month Phase 2a dose finding, POC Study indicate that elagolix 300 mg BID was the most effective dose in reducing HMB associated with uterine fibroids. The 6-month Phase 2b safety/efficacy study confirmed these results and also demonstrated that E2/NETA (estradiol 1.0 mg/norethindrone acetate 0.5 mg) QD was effective in preventing BMD loss and ameliorating vasomotor symptoms due to estrogen suppression. The data (PK/PD) from the multiple ascending dose (MAD) and folliculogenesis studies in healthy subjects also provide additional support for the targeted elagolix dose. All of these studies have demonstrated an acceptable safety and tolerability profile to date.

Based on the totality of safety and efficacy data, elagolix 300 mg BID with E2/NETA (estradiol 1.0 mg/norethindrone acetate 0.5 mg) QD was selected for further evaluation in Phase 3. The maximum elagolix dose administered in this study will not exceed a total daily dose of 600 mg.

6.0 Complaints

A Complaint is any written, electronic, or oral communication that alleges deficiencies related to the physical characteristics, identity, quality, purity, potency, durability, reliability, safety, effectiveness, or performance of a product/device after it is released for distribution.

Complaints associated with any component of this investigational product must be reported to the Sponsor (Section 6.2.2). For adverse events, please refer to Section 6.1 through 6.1.5. For product complaints, please refer to Section 6.2

All adverse events will be followed to a satisfactory conclusion.

6.1 Medical Complaints

The investigator will monitor each subject for clinical and laboratory evidence of adverse events on a routine basis throughout the study. The investigator will assess and record any adverse event in detail including the date of onset, event diagnosis (if known) or sign/symptom, severity, time course (end date, ongoing, intermittent), relationship of the adverse event to study drug, and any action(s) taken. For serious adverse events considered as having "no reasonable possibility" of being associated with study drug, the investigator will provide an Other cause of the event. For adverse events to be considered intermittent, the events must be of similar nature and severity. Adverse events, whether in response to a query, observed by site personnel, or reported spontaneously by the subject will be recorded.

6.1.1 Definitions

6.1.1.1 Adverse Event

An adverse event (AE) is defined as any untoward medical occurrence in a patient or clinical investigation subject administered a pharmaceutical product and which does not necessarily have a causal relationship with this treatment. An adverse event can therefore be any unfavorable and unintended sign (including an abnormal laboratory finding), symptom, or disease temporally associated with the use of a medicinal (investigational) product, whether or not the event is considered causally related to the use of the product.

Such an event can result from use of the drug as stipulated in the protocol or labeling, as well as from accidental or intentional overdose, drug abuse, or drug withdrawal. Any worsening of a pre-existing condition or illness is considered an adverse event. Worsening in severity of a reported adverse event should be reported as a new adverse event. Laboratory abnormalities, and vital signs are considered to be adverse events only if they result in discontinuation from the study, necessitate therapeutic medical intervention and/or if the investigator considers them to be adverse events.

An adverse event of amenorrhea will be reported for subjects who do not return to menses by the Post-Treatment Follow-up Month 2 Phone Visit and the adverse event will be followed until resolution. The onset date of the adverse event will be the date of the Follow-up Month 2 Visit.

A BMD decrease at any anatomic location (spine, total hip or femoral neck) during the Treatment or Post-Treatment Follow-up period that leads to discontinuation from study or a BMD decrease at any anatomic location with a T-score < -1.5 should be reported as an adverse event.

An elective surgery/procedure scheduled to occur during a study will not be considered an adverse event if the surgery/procedure is being performed for a pre-existing condition and the surgery/procedure has been pre planned prior to study entry. However, if the pre-existing condition deteriorates unexpectedly during the study (e.g., surgery performed earlier than planned), then the deterioration of the condition for which the elective surgery/procedure is being done will be considered an adverse event.

6.1.1.2 Serious Adverse Events

If an adverse event meets any of the following criteria, it is to be reported to AbbVie as a serious adverse event (SAE) within 24 hours of the site being made aware of the serious adverse event.

Death of Subject	An event that results in the death of a subject.
Life-Threatening	An event that, in the opinion of the investigator, would have resulted in immediate fatality if medical intervention had not been taken. This does not include an event that would have been fatal if it had occurred in a more severe form.
Hospitalization or Prolongation of Hospitalization	An event that results in an admission to the hospital for any length of time or prolongs the subject's hospital stay. This does not include an emergency room visit or admission to an outpatient facility.
Congenital Anomaly	An anomaly detected at or after birth, or any anomaly that results in fetal loss.

Persistent or Significant Disability/Incapacity	An event that results in a condition that substantially interferes with the activities of daily living of a study subject. Disability is not intended to include experiences of relatively minor medical significance such as headache, nausea, vomiting, diarrhea, influenza, and accidental trauma (e.g., sprained ankle).
Important Medical Event Requiring Medical or Surgical Intervention to Prevent Serious Outcome	An important medical event that may not be immediately life-threatening or result in death or hospitalization, but based on medical judgment may jeopardize the subject and may require medical or surgical intervention to prevent any of the outcomes listed above (i.e., death of subject, life-threatening, hospitalization, prolongation of hospitalization, congenital anomaly, or persistent or significant disability/incapacity). Additionally, any elective or spontaneous abortion or stillbirth is considered an important medical event. Examples of such events include allergic bronchospasm requiring intensive treatment in an emergency room or at home, blood dyscrasias or convulsions that do not result in inpatient hospitalization, or the development of drug dependency or drug abuse.

For serious adverse events with the outcome of death, the date and cause of death will be recorded on the appropriate case report form.

6.1.1.3 Adverse Events of Special Interest

Some adverse events, such as adverse events of special interest (AESI), such as rash/hypersensitivity, fracture, neuro-psychiatric (depression, mood swings, etc.), vasomotor symptoms (hot flush, night sweats) or serious adverse events. AbbVie may require additional information, including family history, to be collected and recorded in the eCRF.

6.1.2 Adverse Event Severity

The investigator will use the following definitions to rate the severity of each adverse event:

Mild	The adverse event is transient and easily tolerated by the subject.
Moderate	The adverse event causes the subject discomfort and interrupts the subject's usual activities.
Severe	The adverse event causes considerable interference with the subject's usual activities and may be incapacitating or life-threatening.

6.1.3 Relationship to Study Drug

The investigator will use the following definitions to assess the relationship of the adverse event to the use of study drug:

Reasonable Possibility	An adverse event where there is evidence to suggest a causal relationship between the study drug and the adverse event.
No Reasonable Possibility	An adverse event where there is no evidence to suggest a causal relationship between the study drug and the adverse event.

For causality assessments, events assessed as having a reasonable possibility of being related to the study drug will be considered "associated." Events assessed as having no reasonable possibility of being related to study drug will be considered "not associated." In addition, when the investigator has not reported a causality or deemed it not assessable, AbbVie will consider the event associated.

If an investigator's opinion of no reasonable possibility of being related to study drug is given, an "Other" cause of event must be provided by the investigator for the serious adverse event.

[figure not shown]
6.1.4 Adverse Event Collection Period

All adverse events reported from the time of study drug administration through Month 6 or Month 12 in the Post-Treatment Follow-Up Period, (if applicable) will be collected, whether solicited or spontaneously reported by the subject. In addition, serious adverse events and protocol-related nonserious adverse events will be collected from the time the subject signed the study-specific informed consent.

If a subject prematurely discontinues from the study, i.e., either prematurely discontinues from Treatment Period and does not enter the Post-Treatment Follow-Up Period or prematurely discontinues from the Post-Treatment Follow-Up Period, adverse events and serious adverse events will be collected up to 30 days after the last dose of study drug.

Adverse event information will be collected as shown in Figure 6.

Figure 6. Adverse Event Collection

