For subjects entering the 12-month Post-Treatment Follow-Up Period, visits will be conducted either by phone or on-site from Month 1 through Month 12. (Subjects who prematurely discontinue from the Treatment Period prior to the Month 3 Study visit, are not required to have the pelvic ultrasound, MRI [if applicable] or DXA [unless the reason for discontinuation was due to BMD decrease or occurrence of fracture] performed in the Post-Treatment Follow-up Period and will complete the study at the Post-Treatment Follow-up Month 6 visit.) Post-Treatment Follow-up Months 1, 3, 6, 9 and 12 are on-site visits while Post-Treatment Follow-up Months 2, 4, 5, 7, 8, 10 and 11 are Phone Visits.

During the phone visits, site personnel will discuss adverse events, concomitant medications, if applicable, obtain the results of the subject's self-administered urine pregnancy test and will remind subjects of the importance of consistent use of appropriate and effective dual non-hormonal contraception through the Post-Treatment Follow-Up Period. Subjects may begin taking hormonal contraception or Tranexamic Acid (Lysteda, Cyklokapron, Cyclo-f) after completing the Post-Treatment Follow-Up Month 2 Visit and having returned to first full menses in the Post-Treatment Follow-up Period.

Subjects will be required to collect sanitary products for the first full menses in the Post-Treatment Follow-up Period. Subjects will return the sanitary products at a Product Collection Visit within approximately 5 days after cessation of bleeding or spotting.

During the Post-Treatment Month 3 and Post-Treatment Month 6 on-site visits, procedures such as TAU, TVU, MRI (if applicable), DXA, clinical safety labs and pregnancy testing will be performed. At the Post-Treatment Period Month 12 visit, procedures including vital signs, lipid panel, Apolipoprotein A and B and DXA will be performed.

Adverse event and concomitant medication review will be conducted at all visits during the Post-Treatment Follow-Up Period, including the phone visits.

Central Laboratory and Central Imaging Vendors:

DXA, Ultrasound, SIS, MRI (if applicable), safety clinical lab samples including Apo A, and Apo B, endocrine panels, and alkaline hematin will be analyzed/evaluated using central laboratories or vendors. Assays for PK, PD and PG will be analyzed at AbbVie.

Analysis of Menstrual Blood Loss:

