PGIC-NBUFS	Patient Global Impression of Change - Non-Bleeding Uterine Fibroid Symptoms
PID	Pelvic Inflammatory Disease
P-gp	P-glycoprotein
РК	Pharmacokinetic
POC	Proof-of-Concept
PRO	Patient Reported Outcome
PSQ	Physician Surgery Questionnaire
PTSD	Post-Traumatic Stress Disorder
QD	Once a day (quaque die)
QoL	Quality of Life
RANKL	Receptor activator of nuclear factor-KB ligand
RBC	Red Blood Cell
RR	Respiration Rate
RNA	Ribonucleic acid
SAE	Serious Adverse Event
SAP	Statistical Analysis Plan
SGOT/ASAT	Serum glutamic-oxaloacetic transaminase/aspartate aminotransferase
SIS	Saline Infusion Sonohysterography
SGPT/ALAT	Serum glutamic-pyruvic transaminase/alanine aminotransferase
SPRM	Selective Progesterone Receptor Modulator
TA MD	Therapeutic Area Medical Director
TAU	Transabdominal Ultrasound
TDD	Total Daily Dose
TBG	Thyroxine-Binding Globulin
TSH	Thyroid Stimulating Hormone
TEAEs	Treatment-emergent adverse events

[figure not shown]
TVU	Transvaginal Ultrasound
UBQ	Uterine Bleeding Questionnaire
UFS-QoL	Uterine Fibroid Symptom Quality of Life Questionnaire
WBC	White Blood Cells
WHO	World Health Organization
WPAI	Work Productivity and Activity Impairment

Pharmacokinetic and Statistical Abbreviations

ANOVA	Analysis of variance
ANCOVA	Analysis of covariance
AUC	Area under the plasma concentration-time curve
C _{max}	Maximum concentration in plasma
LOCF	Last Observation Carried Forward
NOAEL	No observed-adverse-effect levels
PD	Pharmacodynamic
РК	Pharmacokinetic
SAP	Statistical Analysis Plan
T _{max}	Time to maximum observed plasma concentration

Definition of Terms

Washout Period (if applicable)	The minimum interval of time for washout of hormonal therapy or other prohibited medications (if applicable).
Screening Period	The approximate 2.5 to 3.5 month period prior to randomization on Day 1, when screening procedures are performed to establish eligibility. Subjects may either enter the Screening Period directly, if no washout is required, or enter after completing the Washout Period (if applicable).
Day 1 (Randomization) or Treatment Period Day 1	The day a subject takes her first dose of study drug. Day 1 will occur between the first and tenth day of the onset (first day with full menstrual flow) of menses.
Monthly Visits: Treatment Period Months 1 through 6 and Post-Treatment Period Months 1 through 12	A month is defined as 28 days.

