8.1.8.2 Adverse Events

Adverse events (AEs) will be coded using the Medical Dictionary for Regulatory Activities (MedDRA) dictionary. Treatment-emergent adverse events (TEAEs) will be summarized for each treatment group. TEAEs are defined as AEs with a start date on or after the first dose of the study drug and within 30 days of the last dose of the study drug. AEs starting more than 30 days following discontinuation of the study drug will not be included in the summaries of TEAEs. AEs starting more than 30 days following discontinuation of the study drug will be summarized separately as Post-Treatment AEs.

When summarizing TEAEs by relationship or severity, if a subject has an event with unknown severity or relationship, then the subject will be counted in the severity/relationship category of "unknown," even if the subject has a second occurrence of the same event with a severity/relationship present. The only exception is if the subject has a second occurrence of the same event with the most extreme severity (i.e., "severe") or a relationship category of "reasonable possibility." In this case, the subject will be counted under these most extreme severity/relationship categories.

Frequencies and percentages of subjects with TEAEs will be calculated for each treatment group as follows:

- Any event
- By system organ class, and preferred term
- By system organ class, preferred term and maximum relationship
- By system organ class, preferred term and maximum severity

- Any event and by system organ class and preferred term for events resulting in study drug discontinuation
- Any event and by system organ class and preferred term for serious events
- Any event and preferred term for AESI's (e.g., hypoestrogenic adverse events)

The Post-Treatment AEs will be summarized in a similar manner as the TEAEs described above.

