12.2 Adverse Events

Adverse events (AEs) will be summarized using system organ classes (SOCs) and preferred terms (PTs) from the Medical Dictionary for Regulatory Activities (MedDRA) Version 19.0 or higher.

For each AE summary, the number and percentage of subjects experiencing at least one AE will be presented. Subjects reporting more than one AE within a SOC will be counted only once for that SOC. Subjects reporting more than one AE for a PT will be counted only once for that PT.

Treatment-emergent AEs are defined as AEs with a start date on or after the first dose of study drug. AEs starting more than 30 days following discontinuation of study drug will not be included in summaries of treatment-emergent AEs. Post-Treatment AEs are defined as AEs starting more than 30 days following discontinuation of study drug in the Treatment Period of this study.

When summarizing AEs by relationship or severity, if a subject has an event with unknown severity or relationship then the subject will be counted in the severity/relationship category of "unknown" even if the subject has a second occurrence of the same event with a severity/relationship present. The only exception is if the subject has a second occurrence of the same event with the most extreme severity (i.e., "severe") or one of the two most extreme relationship categories (i.e., "probably related" or "possibly related"). In this case, the subject will be counted under these most extreme severity/relationship categories.

Treatment Period

The number and percentage of subjects with treatment-emergent AEs will be calculated by treatment group as follows:

- Any AEs
- Any AEs by system organ class (SOC) and preferred term (PT)
- Any AEs occurring in $\geq 5\%$ of subjects by system organ class (SOC) and preferred term (PT)
- Any AEs by PT in descending frequency of elagolix 300 mg BID plus E2/NETA treatment group
- Any AEs by maximum severity
- Any AEs by maximum relationship
- Any AEs reasonably possibly related to study drug
- Any AEs leading to study drug discontinuation
- Any serious AEs (SAEs)
- Any SAEs reasonably possibly related to study drug

- Any SAEs leading to study drug discontinuation
- Any AEs of special interest as specified in [Appendix Q](#)
- Any AEs leading to death

A listing by treatment group of treatment-emergent AEs with subject IDs will be generated. Listings of all treatment-emergent SAEs, AEs leading to death, and AEs leading to study drug discontinuation will be generated.

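### Protocol 6.1.4 stops AE and SAE collection 30 days after the last dose for women who leave follow-up early, which contradicts other protocol rules and puts events found at exit at risk

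*Protocol*

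**What the plan says.** Protocol 6.1.4 (Adverse Event Collection Period) contains two rules. The general rule covers "All adverse events reported from the time of study drug administration through Month 6 or Month 12 in the Post-Treatment Follow-Up Period". The second paragraph sets an exception for early leavers and names two groups: women who stop treatment and never enter follow-up, and any woman who "prematurely discontinues from the Post-Treatment Follow-Up Period". For both groups, "adverse events and serious adverse events will be collected up to 30 days after the last dose of study drug".

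Other sections speak to the same women:

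- Synopsis: "Adverse event and concomitant medication review will be conducted at all visits during the Post-Treatment Follow-Up Period", phone visits included.
- Section 5.4.1 sends a woman who leaves follow-up to a Post-Treatment Premature Discontinuation Visit. The Appendix C column for that visit marks AE monitoring and a DXA scan.
- Section 6.1.1.1, repeated in the DXA text of 5.3.1.1, makes a BMD decrease an AE if it occurs "during the Treatment or Post-Treatment Follow-up period that leads to discontinuation from study".
- Section 6.1.6 requires a woman who conceives during follow-up to be discontinued. It still treats abortion, stillbirth or congenital anomaly as an SAE, reportable within 24 hours of the site learning of it.

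On the analysis side, protocol 8.1.8.2 states that "AEs starting more than 30 days following discontinuation of the study drug will be summarized separately as Post-Treatment AEs", and SAP 12.2 uses the same boundary: "Post-Treatment AEs are defined as AEs starting more than 30 days following discontinuation of study drug".

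**The concern.** A 30-day limit suits women who never enter follow-up, because it matches the end of the treatment-emergent window. Applied to women already in follow-up, it sets a closing date that most of them will have passed before they leave. A site that follows 6.1.4 when closing out such a woman has a written reason not to record what it finds at her exit visit. Other sections give it a written reason to record the same finding.

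At stake is the safety record at the point of exit. Some exits are caused by events: the protocol itself provides for a BMD loss that ends participation, and requires discontinuation for pregnancy. These are cases in which the reason for leaving, or what follows from it, is a reportable event.

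**Working it through.** The plan states no figure to reproduce. The check is a comparison of dates and rules.

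**Inputs.** Cut-off for early leavers: day 30 after the last dose (6.1.4). Month length: "A month is defined as 28 days" (1.3). Follow-up visit window: ±7 days (Table 1). Follow-up Month 6 DXA window: −15 to +4 days (Table 1). Post-Treatment AE window: more than 30 days after stopping drug (8.1.8.2; SAP 12.2). I count follow-up months from the last dose, as the SAP windows do.

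**Step 1. Cut-off against the analysis window.** Collection for early leavers covers days 1 to 30. Post-Treatment AEs start at 30 + 1 = day 31. As worded, the two do not overlap on any day.

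**Step 2. Cut-off against scheduled follow-up events.**

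| Event | Nominal day | Earliest in window | Earliest minus day 30 |
|---|---|---|---|
| Month 1 visit | 1 × 28 = 28 | 28 − 7 = 21 | −9 |
| Month 2 visit | 2 × 28 = 56 | 56 − 7 = 49 | 19 |
| Month 6 DXA | 6 × 28 = 168 | 168 − 15 = 153 | 123 |

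Only the Month 1 visit can fall inside the limit. The first scheduled follow-up DXA comes at least 123 days after it (168 − 30 = 138 at the nominal day). A DXA at a discontinuation visit could come sooner for a woman who leaves at once.

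**Step 3. The rules side by side, for a woman leaving after day 30.**

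- General rule of 6.1.4: collect through Month 6 or 12. Exception in 6.1.4: collection has already ended.
- Synopsis, 5.4.1 and Appendix C: review AEs at each visit and at the exit visit. 6.1.4 exception: an AE starting after day 30 is outside collection.
- 6.1.1.1: report the BMD loss that made her leave. 6.1.4 exception: a loss found at the scheduled Month 6 or Month 12 scan is past the limit.
- 6.1.6: report the pregnancy-outcome SAE whenever the site learns of it. 6.1.4 exception: no SAE after day 30.

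Sections 5.4.1 and 6.0 require AEs to be followed to a satisfactory conclusion, but that concerns events already recorded and not new ones.

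**Step 4. What is realistically exposed.** Follow-up visits, by phone or on site, are monthly. For a woman who attended every scheduled visit, the time since her last AE review is nominally 28 days. With one visit at its earliest and the next at its latest it is 28 + 7 + 7 = 42 days. It is longer if she missed visits. Section 5.4.1 asks for the exit visit as soon as possible and sets no window for it in follow-up.

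**The case against.** The strongest reply is that no site can apply the exception backwards. At the Month 2 visit nobody knows that a woman will leave at Month 8. Her AEs are reviewed and recorded then under the general rule, and nothing in either document says to delete them later. SAP 12.2 classifies AEs by start date alone and excludes no follow-up dropouts. Sections 6.1 and 6.1.5 also require monitoring throughout the study and SAE notification within 24 hours of awareness, with no 30-day limit. Figure 6, to which 6.1.4 refers, is not in the text available and may clarify the rule.

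Most of this stands, and it limits the point. From Steps 1 and 2 a reader might infer that early leavers can supply no Post-Treatment AE, that nearly all their follow-up time is lost to safety collection, or that Post-Treatment AE rates are biased low because these women stay in the denominator without their events. The documents do not support that. It would need already recorded events to be discarded, and SAP 12.2 gives no separate denominator for the post-treatment summaries.

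Nor does the rule threaten the assessment of recovery. Follow-up BMD comes from DXA data (SAP 12.4.2), and time to first menses comes from alkaline hematin data (SAP 11.3.5.4).

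The amenorrhea AE, with onset at the Month 2 visit, is a weak example because it is normally recorded while the woman is still in follow-up. The BMD conflict is narrower than it looks: 5.4 lists no BMD withdrawal criterion, so such an exit would rest on the general judgement clauses.

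The reply does not remove the contradiction. The exception names women who leave follow-up, so it cannot be read as covering only those who never enter. Pointing to 6.1.5, 6.1.6 and Appendix C shows that the protocol gives opposing instructions; it does not show which one a site will follow at close-out.

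**Conclusion.** The point holds as a contradiction in the protocol with a limited practical effect. For women leaving follow-up after day 30, the AE and SAE limit in 6.1.4 precedes their exit and conflicts with its own general rule, the visit schedule, 6.1.1.1 and 6.1.6.

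The likely loss is confined to AEs and SAEs found at the exit visit or arising since the last attended visit, and to inconsistent recording between sites. Those events would enter the Post-Treatment summaries, for which SAP 12.2 plans only any AE and any SAE, and SAP 12.1 rules out testing in follow-up. Treatment-emergent AEs, whose window ends at 30 days, and the efficacy analyses are unaffected.

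This rests on two assumptions: that sites keep what they recorded before exit, and that Figure 6 does not already resolve the wording. The number of women who leave follow-up early is not given, so the number of events at risk cannot be estimated. The wording should still be corrected, because it is a stated safety-collection rule that would lose events if followed.

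**What to change.** Amend the second paragraph of 6.1.4 to separate the two groups:

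- Women who stop treatment and do not enter follow-up: AEs and SAEs to 30 days after the last dose, as now.
- Women who leave follow-up early: AEs and SAEs through the Post-Treatment Premature Discontinuation Visit, or last contact if that visit does not take place, or 30 days after the last dose, whichever is later.

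Add that pregnancy outcomes continue to be reported under 6.1.6. Check the result against 6.1.1.1 and Appendix C, and correct Figure 6 if it repeats the present rule.

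The cost is about one sentence in an amendment and a note to sites. No visit or procedure is added, because AE monitoring is already scheduled at the follow-up discontinuation visit. The SAP definitions need no change.
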